7.5 TREATMENT GROUPS

The analyses will be conducted by treatment group:

- HB-1
- Placebo

7.6 STATISTICAL HYPOTHESIS TESTS

The hypotheses for testing the primary analysis are:

$$H_0: \mu_a = \mu_p \text{ vs. } H_a: \mu_a \neq \mu_p$$

where μ_a is the mean change from baseline to Week 12 in the PDSS for the HB-1 arm and μ_p is the mean change from baseline to week 12 in the placebo arm.

Testing will be done at the 0.05 alpha-level. Any confidence intervals (CI) provided will be at 95% confidence.

7.7 MISSING DATA

Data may be missing either because an assessment is not completed or if patients have withdrawn consent from further participation in the study. To minimize missing data, participants who may discontinue treatment, but do not withdraw consent from further participation are expected to continue in the study, with primary and key secondary efficacy assessments conducted.

The approach to handling missing data for the primary endpoint and key secondary endpoints is dependent upon the extent of missing data and potential reasons for missingness. Therefore, prior to database lock, an assessment of missing data will be conducted to determine potential reasons for missingness, where missing data will be considered missing not at random (MNAR), unless sufficient evidence is available to reasonably conclude the data is missing at random (MAR).

The mixed model analysis is considered valid under a missing at random assumption, however alternative approaches such as multiple imputation using within-treatment group imputation, control-based imputation and a tipping point analysis with a within-treatment imputation will be considered if a sufficient amount of missing data are present and considered potentially MNAR.

7.8 MULTIPLICITY ADJUSTMENTS

To control for multiplicity of select analyses, Hochberg's procedure will be used to test the protocol designated primary endpoint (PDSS) as well as the key secondary endpoint CGI-S,

which are not expected to be negatively correlated. Accordingly, if the largest p-value among these two endpoints (at the primary time point) does not exceed 0.05, then both endpoints will be considered statistically significant. If the largest p-value exceeds 0.05 and the smallest p-value does not exceed 0.025, then the endpoint with the smaller p-values will be considered statistically significant. This provides control of the familywise error rate at $\alpha = 0.05$ such that either of the 2 endpoints statistically significant according to the above procedure will constitute a successful efficacy outcome for the trial.

Irrespective of the significance of these specific measures, planning for future studies will be based on the totality of safety and efficacy data and nominal p-values will be reported for all inferential tests.

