6.9 EFFICACY

6.9.1 PRIMARY AND SECONDARY EFFICACY ENDPOINTS

- Change in Panic Disorder Symptom Severity Scale (PDSS)- primary efficacy endpoint.
- Number of panic attacks
- Change in Clinical Global Impression-Severity Scale (CGI-S)
- Change in Quality-of-Life Enjoyment and Satisfaction Questionnaire Short Form (Q-LES-Q-SF)
- Change in Leibowitz Social Anxiety Scale (LSAS)
- Change in Assessment of Overall Sleep Quality -- Question #6 from the Pittsburgh Sleep Quality Index

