7.11 EFFICACY AND EXPLORATORY ANALYSES

7.11.1 PRIMARY AND SECONDARY EFFICACY ENDPOINTS

- Panic Disorder Symptom Severity Scale (PDSS)- primary efficacy endpoint
- Number of panic attacks – key secondary endpoint
- Clinical Global Impression-Severity Scale (CGI-S) – key secondary endpoint
- Quality-of-Life Enjoyment and Satisfaction Questionnaire Short Form (Q-LES-Q-SF)
- Leibowitz Social Anxiety Scale (LSAS)
- Assessment of Overall Sleep Quality -- Question #6 from the Pittsburgh Sleep Quality Index

The primary analysis of efficacy will be performed using the ITT population. The change from baseline to in PDSS will be compared between HB-1 and placebo using Mixed Model Repeated Measures (MMRM) model using SAS mixed procedure with repeated measures. The model will include the fixed effect of treatment, visit, the treatment-by-visit interaction, baseline, baseline-by-visit. The outcome will be the change from baseline to each on-treatment time point. All protocol-scheduled time points will be included in the model. The model will use the unstructured or Toeplitz (whichever has a better fit by AICC value) within-subject variance-covariance matrix. The denominator degrees of freedom will be according to the method of Kenward-Roger. The estimated least square (LS) means and their standard errors as well as the estimated treatment effect (differences between treatments at each time point) will be summarized by treatment. In addition, the 95% CIs of the LS means and the difference between treatments, p-values for treatment comparisons will be provided. The primary analysis

timepoint will be at 12 weeks. Secondary endpoints will be analyzed similarly. For endpoints without a baseline measurement, baseline and the visit-by-baseline interaction will be omitted from the model.

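### SAP 7.8 lets CGI-S alone make the trial an efficacy success, although PDSS is the only primary endpoint, the only stated hypothesis and the only powered endpoint

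*SAP*

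**What the plan says.** **Labels.** SAP 6.9.1 lists "Change in Panic Disorder Symptom Severity Scale (PDSS)- primary efficacy endpoint". SAP 7.11.1 repeats that label and lists "Clinical Global Impression-Severity Scale (CGI-S) – key secondary endpoint". Section 7.8 itself still refers to PDSS as the primary endpoint designated by the protocol.

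**Hypothesis.** SAP 7.6 sets out one primary hypothesis, equality against inequality of two means, the first of which "is the mean change from baseline to Week 12 in the PDSS for the HB-1 arm". CGI-S has no stated hypothesis.

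**Power.** SAP 7.4 rests on PDSS alone: 80 patients, difference 3.75, SD 4.5, alpha 0.05, power above 95%.

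**Decision rule.** Under SAP 7.8, both endpoints are significant "if the largest p-value among these two endpoints (at the primary time point) does not exceed 0.05". "If the largest p-value exceeds 0.05 and the smallest p-value does not exceed 0.025", only the endpoint with the smaller p-value is significant. The section then states that "either of the 2 endpoints statistically significant according to the above procedure will constitute a successful efficacy outcome for the trial".

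**Protocol.** Section 9.1, under the multiplicity heading, sets a fixed order with each test at 0.05: PDSS, then number of panic attacks, then CGI-S.

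**Declared change.** SAP Section 8 records the move to Hochberg. It describes a family of three endpoints (PDSS, panic attacks, CGI-S) where 7.8 has two, and it does not mention the new definition of success.

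**The concern.** Under the protocol, no confirmatory claim could be made on CGI-S after PDSS had failed. Under SAP 7.8, a trial whose primary hypothesis is not rejected can still be declared successful on an endpoint that the same document calls secondary. In effect CGI-S becomes a second primary endpoint without the label, a hypothesis or a power statement.

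What is at stake is the meaning of the headline result. A success declared under 7.8 would not tell the reader whether PDSS differed between the arms. A reader who looked only at the list of changes in Section 8 would not learn that the criterion for success had changed.

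**Working it through.** **Inputs from the documents.** 40 patients per arm (80 at 1:1, SAP 6.2); difference 3.75 and SD 4.5 (SAP 7.4); two-sided alpha 0.05 (SAP 7.6; protocol synopsis, Statistical Methodology); Hochberg thresholds 0.05 and 0.025 (SAP 7.8).

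**Assumptions.** The true CGI-S effect and the correlation between the two test statistics are not in the documents. SAP 7.8 says only that the endpoints are ones "which are not expected to be negatively correlated". Ranges are therefore shown. A normal approximation is used, with no dropout.

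**1. The plan's own power.** Standardised effect 3.75/4.5 = 0.833. Mean z = 0.833 × √(40/2) = 3.727. Power at two-sided 0.05 = Φ(3.727 − 1.960) = 96.1%, or 95.7% from the noncentral t with 78 df. The stated figure of more than 95% is reproduced.

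**2. Familywise error.** For two independent null endpoints, P(any success) = 0.05² + 2 × 0.025 × 0.95 = 0.0025 + 0.0475 = 0.050. It falls to 0.048 at correlation 0.5 and 0.042 at 0.9. The SAP's statement "This provides control of the familywise error rate at" 0.05 is correct for the two-endpoint family.

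**3. What CGI-S-only success means.** If PDSS has p ≤ 0.05 and CGI-S has p ≤ 0.025, the larger p-value is at most 0.05 and both endpoints pass. Success on CGI-S alone therefore always means PDSS p > 0.05 and CGI-S p ≤ 0.025. The primary hypothesis would not have been rejected even at the full 0.05.

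**4. How often.** The quantity is P(|z_PDSS| < 1.960 and |z_CGI-S| ≥ 2.241), with each mean z equal to the effect in SD units × √20.

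| Assumed effects (PDSS / CGI-S) | Mean z | Correlation | CGI-S-only success |
|---|---|---|---|
| 0.83 / 0.83 (design effect on both) | 3.73 / 3.73 | 0 to 0.8 | 3.6% to 1.4% |
| 0.4 / 0.4 | 1.79 / 1.79 | 0.5 to 0.8 | 11.0% to 5.3% |
| 0 / 0.5 | 0 / 2.24 | 0 to 0.8 | 47% |
| 0 / 0 | 0 / 0 | 0 to 0.9 | 2.4% to 0.6% |

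The third row can be checked by hand at zero correlation: P(CGI-S p ≤ 0.025) = Φ(2.236 − 2.241) ≈ 0.498, and 0.498 × 0.95 = 0.473.

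**5. Effect on the power of PDSS itself.** When CGI-S gives no support, PDSS must reach 0.025: Φ(3.727 − 2.241) = 93.1% (noncentral t 92.3%). If CGI-S has no true effect and is independent of PDSS, the full Hochberg power for PDSS is 0.931 + 0.05 × (0.961 − 0.931) = 93.3%. That is below the stated 95%, whereas PDSS tested first at 0.05 keeps 96.1%.

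**The case against.** The strongest defence is that this is an explicit rule, fixed in advance, with valid error control. Section 8 announces the Hochberg procedure, and success on either of two endpoints is a legitimate design. All of that stands. A reader might infer that 7.8 inflates the false-positive rate; step 2 shows that it does not. But error control does not settle what success means when the designated primary endpoint fails, and an either-endpoint design needs both endpoints declared primary.

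It can also be said that 7.8 claims a successful efficacy outcome, not that the primary endpoint was met; that the primary objective is worded as safety and efficacy in general; and that 7.8 bases planning of future studies on the totality of the data and reports nominal p-values throughout. This softens the practical consequence. It does not remove the sentence that defines trial success.

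A second inference is that, because the p-values are two-sided and 7.8 carries no sign condition, a result favouring placebo could count as success, or a worsening on CGI-S could rescue a PDSS p-value between 0.025 and 0.05. The text does lack the condition. However, the protocol's synopsis and background hypothesise a reduction in severity relative to placebo, and efficacy success cannot sensibly mean harm. The rescue is also negligible: with no effect on either endpoint and zero correlation its probability is 0.0125 × 0.025 ≈ 0.03%, and less with positive correlation. This is a drafting gap, not a material risk.

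Finally, the larger percentages depend on effects that the plan does not assume. That is fair, and the design-effect row gives the plan's own PDSS scenario.

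**Conclusion.** The point holds as an internal contradiction. The success rule in SAP 7.8 does not match the primary endpoint, hypothesis and sample size in 6.9.1, 7.11.1, 7.6 and 7.4, and it departs from the protocol's sequence in a way that Section 8 does not disclose.

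Its size depends on the unknown CGI-S effect and correlation. If PDSS performs as designed and CGI-S has the same effect, few trials are affected (1.4–3.6%). With smaller equal effects the share is 5–11%, and it approaches half if only CGI-S responds. No document supports that last split; it marks the case in which the rule decides the outcome. The rule matters most when PDSS underperforms, which is when the definition of success must be clear.

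The Section 8 family of three would not cure this. CGI-S alone would then need p ≤ 0.05/3 = 0.0167, and the same objection would apply.

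**What to change.** Amend the SAP before unblinding, in one of two ways.

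**Preferred.** In 7.8, state that primary efficacy success requires PDSS to be significant in favour of HB-1, tested first at two-sided 0.05 as in protocol Section 9.1. A significant CGI-S with non-significant PDSS is reported as such, with the primary endpoint not met. Cost: the CGI-S-only route to success is given up. PDSS keeps about 96% power and the sample size need not change. Keeping Hochberg while requiring PDSS would be a poorer version, since PDSS power drops to about 93% when CGI-S has no effect.

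**Alternative.** If either endpoint is meant to suffice, name PDSS and CGI-S as dual primary endpoints in 6.9.1, 7.6 and 7.11.1, add the CGI-S hypothesis, and restate the PDSS power under Hochberg in 7.4. Cost: the stated power above 95% may no longer hold for PDSS.

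**In either case.** Add the words *in favour of HB-1* to the success clause; two-sided p-values can stay. Reconcile Section 8 with 7.8 on whether the family has two or three endpoints and where panic attacks stand, and list the definition of success among the changes from the protocol. These are wording changes only.

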7.9 INTERIM ANALYSIS

Interim analyses are not planned for this study.

7.10 ENDPOINTS AND ESTIMANDS

Endpoints are based on measurement scales collected over the visits of the study. Each of the scales may have domains or subdomains. The treatment policy strategy is planned for all intercurrent events.

7.11 EFFICACY AND EXPLORATORY ANALYSES

7.11.1 PRIMARY AND SECONDARY EFFICACY ENDPOINTS

- Panic Disorder Symptom Severity Scale (PDSS)- primary efficacy endpoint
- Number of panic attacks – key secondary endpoint
- Clinical Global Impression-Severity Scale (CGI-S) – key secondary endpoint
- Quality-of-Life Enjoyment and Satisfaction Questionnaire Short Form (Q-LES-Q-SF)
- Leibowitz Social Anxiety Scale (LSAS)
- Assessment of Overall Sleep Quality -- Question #6 from the Pittsburgh Sleep Quality Index

The primary analysis of efficacy will be performed using the ITT population. The change from baseline to in PDSS will be compared between HB-1 and placebo using Mixed Model Repeated Measures (MMRM) model using SAS mixed procedure with repeated measures. The model will include the fixed effect of treatment, visit, the treatment-by-visit interaction, baseline, baseline-by-visit. The outcome will be the change from baseline to each on-treatment time point. All protocol-scheduled time points will be included in the model. The model will use the unstructured or Toeplitz (whichever has a better fit by AICC value) within-subject variance-covariance matrix. The denominator degrees of freedom will be according to the method of Kenward-Roger. The estimated least square (LS) means and their standard errors as well as the estimated treatment effect (differences between treatments at each time point) will be summarized by treatment. In addition, the 95% CIs of the LS means and the difference between treatments, p-values for treatment comparisons will be provided. The primary analysis

timepoint will be at 12 weeks. Secondary endpoints will be analyzed similarly. For endpoints without a baseline measurement, baseline and the visit-by-baseline interaction will be omitted from the model.

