^l Safety Follow-up Phone Call is performed approximately 7 days after Visit 6/EOS.

^m Only the PDSS will be repeated at the Week 2 visit.

ⁿ Placebo-Control Reminder Script (PCRS) (Cohen, EA. 2021). The PCRS will be administered immediately prior to administering the PDSS at Visits 3-6.

^o CogScreen Symbol Digit Coding Test (SDC) (Kay G. 1995); SDC to be done twice at Screening/Visit 1 and no passing score is required.

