7.4 SAMPLE SIZE DETERMINATION

Assuming a standard deviation of 4.5 for the PDSS, 80 patients will provide more than 95% power to detect a difference in the mean change (from baseline) in the PDSS score of 3.75 at an

alpha-level of 0.05 at 12 weeks. This corresponds to a 50% reduction in mean PDSS scores on HB-1 and a 25% reduction in mean PDSS scores on placebo, assuming baseline mean PDSS scores of 15 for both groups.

In addition, with respect to adverse events, the study has approximately 95% power to detect at least one patient with an event that occurs in 7.2% of patients in either treatment group.

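### If the unnamed Toeplitz structure is the common-variance type, AICC can pool the Week 12 variance over visits and modestly misstate the CGI-S test, and the PDSS test mainly under near-flat correlation or falling SDs

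*SAP*

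**What the plan says.** SAP 7.11.1 specifies a "Mixed Model Repeated Measures (MMRM) model using SAS mixed procedure with repeated measures" for the change in PDSS, with Week 12 as the primary time point and secondary endpoints analysed similarly. On the mean structure: "The model will include the fixed effect of treatment, visit, the treatment-by-visit interaction, baseline, baseline-by-visit". On the covariance: "The model will use the unstructured or Toeplitz (whichever has a better fit by AICC value) within-subject variance-covariance matrix". On inference: "The denominator degrees of freedom will be according to the method of Kenward-Roger". Protocol 9.1 (Efficacy and Exploratory Analyses) gives the same covariance rule. Neither document says whether Toeplitz means one variance for all visits or one per visit, and neither gives a fallback for non-convergence.

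The visit schedule differs by endpoint. SAP 6.5, footnote m: "Only the PDSS will be repeated at the Week 2 visit". So among the efficacy questionnaires PDSS has four post-baseline visits (Weeks 2, 4, 8, 12) and CGI-S has three (Weeks 4, 8, 12).

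SAP 7.8 applies Hochberg's procedure to PDSS and CGI-S, and "either of the 2 endpoints statistically significant according to the above procedure will constitute a successful efficacy outcome for the trial". SAP section 8 (Changes from Protocol) describes the Hochberg family as also containing the number of panic attacks.

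**The concern.** The decisive test is the treatment contrast at one visit, Week 12. The unstructured matrix gives that visit its own variance. Plain Toeplitz replaces it with a variance common to all visits. If the SD at Week 12 is larger than at earlier visits, the standard error is too small and the test is liberal; if it is smaller, the test is conservative. Kenward-Roger allows for estimating the covariance parameters within the chosen structure. It does not correct a wrong structure.

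AICC removes the badly wrong cases, because a large variance change makes it choose unstructured. With 80 patients it does not reliably remove mild or moderate change, because its penalty favours the smaller structure. Hochberg's control at 0.05 needs valid p-values for each endpoint at Week 12, and one of the two permitted covariance outcomes may not deliver them.

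**Working it through.** **1. The plan's own figure.** SAP 7.4: "Assuming a standard deviation of 4.5 for the PDSS, 80 patients will provide more than 95% power" for a difference of 3.75. With 40 per arm, SE = 4.5 × √(2/40) = 1.006 and 3.75/1.006 = 3.727. Normal power = Φ(3.727 − 1.960) = 96.1%; noncentral t with 78 df gives 95.7%. The stated figure reproduces.

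**2. How strongly AICC leans to Toeplitz.** The AICC penalty is 2kn/(n − k − 1), with k covariance parameters and n = 80 × visits − 3 × visits (intercept, treatment and baseline at each visit).
- PDSS, n = 308: unstructured, k = 10, 20.74; Toeplitz, k = 4, 8.13. Gap 12.61.
- CGI-S, n = 231: unstructured, k = 6, 12.38; Toeplitz, k = 3, 6.11. Gap 6.27.

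Unstructured is chosen only if it improves −2 log-likelihood by more than the gap.

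**3. What pooling does.** Take assumed PDSS SDs of 3.8/3.8/3.9/4.5. The pooled SD is √[(14.44 + 14.44 + 15.21 + 20.25)/4] = √16.085 = 4.01. Then 4.01/4.5 = 0.891, so the standard error is 11% too small. If Toeplitz were always used, the effective critical value would be about 1.96 × 0.891 = 1.747, a two-sided error near 8.1%. AICC avoids part of this by sometimes choosing unstructured.

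**4. Type I error of the whole rule, complete data.** The residual cross-product matrix was drawn as Wishart with 80 − 3 = 77 df, 4,000 draws per scenario, with REML fits of both structures. Visit SDs and correlations are assumptions. The correlations were: decay of 0.70 or 0.85 per 4 weeks; a mixture, 0.5 + 0.5 × the 0.70 decay; and flat at 0.4, 0.6 or 0.7. Unstructured gives 5.0% by theory. Monte Carlo error is at most 0.025 points.

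| PDSS SDs, Weeks 2/4/8/12 | Decaying or mixed | Flat |
|---|---|---|
| 3.8/3.8/3.9/4.5 | 5.1% to 5.2% | 6.4% to 6.9% |
| 4.0/4.2/4.4/4.5 | 5.1% to 5.2% | 5.9% to 6.0% |
| 3.3/3.7/4.2/4.5 | 5.0% | 5.3% to 5.9% |

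For the top row with flat correlation, Toeplitz was chosen in 55% to 72% of draws. Falling SDs (5.2/5.0/4.7/4.5 and 5.8/5.4/4.9/4.5) gave 4.0% to 4.7% over all correlations. Constant SD gave 5.0%.

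For CGI-S, with the same relative SDs at Weeks 4, 8 and 12, rising SDs gave 5.4% to 5.8% (decaying or mixed) and 5.5% to 6.1% (flat). Falling SDs gave 4.3% to 4.6%, and constant SD 5.0%.

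The endpoints differ because PDSS visits are 2, 4 and 4 weeks apart. Correlation that decays in real time is then not Toeplitz, AICC tends to reject the structure, and for rising SDs the harm largely goes. CGI-S visits are evenly spaced, so decaying correlation is itself Toeplitz and gives little such protection.

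**5. A second simulation** used SDs rising linearly in visit order by 20% in total. With correlation that is Toeplitz in visit order, PDSS error was 6.3% to 6.6% and CGI-S 5.7% to 6.2%. With PDSS correlation decaying 0.7 per 4 weeks in real time, PDSS error was 5.0% to 5.2% for SD rises of 10% to 30%.

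**6. Hochberg on PDSS and CGI-S only**, assumed endpoint correlation 0.3 to 0.8 (mixed visit correlation not run). Familywise error is 4.3% to 5.0% with unstructured. Under the rule it is 4.8% to 6.6% for rising SDs (+0.3 to +1.8 points) and 3.6% to 4.4% for falling SDs (−0.4 to −0.9). For constant SD it changes by no more than 0.1 point.

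**7. Missing data, PDSS only**, one assumed dropout model with 20% missing at Week 12. Rule minus unstructured: 3.8/3.8/3.9/4.5, +2.0 points (flat 0.6) and +0.2 (decay 0.85); 4.0/4.2/4.4/4.5, +0.9 (flat 0.6) and +0.35 (decay 0.70); 5.2/5.0/4.7/4.5, −1.0 (flat 0.6) and −0.4 (decay 0.85); constant SD, 0.0 to +0.1. Mean bias of the estimate is at most 0.03 PDSS points. These figures have no second calculation behind them.

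**The case against.** The strongest reply is that the certain defect is only an unnamed covariance type. If the sponsor meant heterogeneous Toeplitz, Week 12 has its own variance and the mechanism does not arise. That stands, and every error rate above is conditional on the plain reading.

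A reader might infer that the rule inflates the type I error of the primary endpoint. The documents do not support that. PDSS inflation needs rising SDs together with correlation close to flat despite the uneven spacing. The top figure of 6.9% also needs almost all of the rise to fall between Weeks 8 and 12. With decaying or mixed correlation and rising SDs the PDSS error is 5.0% to 5.2%, and with falling SDs the test is conservative. The documents give no visit SDs or correlations, so neither direction nor size is known.

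A reader might also quote 6.6% as the trial's familywise error. That figure assumes the two-endpoint family of SAP 7.8. Section 8 adds the number of panic attacks, so the figure is conditional until the two sections are reconciled.

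Nor does the rule leave the analyst free to choose: it is prespecified and mechanical. The stated power is not in question.

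These replies limit the size of the problem. They give no reason to keep the AICC choice, whose only gain is a small increase in degrees of freedom.

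**Conclusion.** The point holds in conditional form. Under the plain reading, the rule can pool the Week 12 variance over visits, and at this sample size AICC does not reliably prevent it. Under mild assumed variance change with complete data, the shift in CGI-S error is about +0.4 to +1.1 points for rising SDs and −0.4 to −0.7 for falling SDs. For PDSS it is +0.3 to +1.9 points for rising SDs with near-flat correlation, at most +0.2 with decaying or mixed correlation, and −0.3 to −1.0 for falling SDs. With constant SD there is no shift.

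With complete data the Week 12 estimate is the same under both structures; only its standard error, interval and p-value change. The missing-data results point the same way but rest on one assumed dropout model and do not cover CGI-S. The change is worth making because it is cheap; the documents do not show that the error rate is materially wrong. Confidence is medium.

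**What to change.** In SAP 7.11.1, prespecify the unstructured matrix with Kenward-Roger for PDSS and the secondary endpoints, and delete the AICC choice. Name one fallback, for non-convergence only: heterogeneous Toeplitz with Kenward-Roger. Used outright with complete data, that fallback gives 4.9% to 5.1% for CGI-S and for PDSS with flat correlation. For PDSS with decaying or mixed correlation it gives about 4.0% to 4.3%, which is conservative.

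The cost is one sentence, with no change to data or sample size. If common-variance Toeplitz were exactly right, power for 3.75 points would be 95.7% with unstructured (77 df, critical t 1.991) against at most 96.0% (209 df, 1.971). That is about 0.3 points, and both exceed the stated 95%.

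If heterogeneous Toeplitz was already intended, naming it is the minimum change and removes the pooled variance. The type I error of an AICC choice between unstructured and heterogeneous Toeplitz was not evaluated, so fixing unstructured is the better course. Separately, SAP 7.8 and section 8 should be reconciled on whether panic attacks belong to the Hochberg family.
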